5. Chronic kidney disease caused by glomerulonephritis, tubulo-interstitial nephritis), Obstructive uropathy or autosomal dominant polycystic kidney, and Kidney disease from other causes

6. Diabetes with HbA1c > 8 or uncontrollable hypertension

7. Active malignancy of cancer in other organs in the last 3 years

8. History of receiving non-steroidal anti-inflammatory drugs (NSAIDs) or other nephrotoxic drugs within the past 1 month (except tenofovir)

(For patients receiving NSAIDs after participating in this study, patients were advised to stop taking NSAIDs but not exclude from the study)

9. Receive immunosuppressive drug

10. Pregnancy

Withdrawal or termination criteria

1. GFR reduction was less than 15 ml / min

2. Receive renal replacement therapy

3. Receive a liver or kidney organ transplant.

4. Request to withdraw from their participation in the study.

5. Develop HCC.

Sample size calculation

From a literature review, It was found that the average value of the eGFR level of the TDF group was -5.34 ± 7.69 (n = 45) (95% CI: -7.65 - -3.02) and the mean value of the eGFR in TAF group was $+2.89. \pm 4.26$ (n = 36) (95% CI: 1.45 - 4.33) But from the Siriraj hospital observations during 2018, the mean The eGFR change value level is +5.92 after TDF dose adjustment. Therefore, from the above data, when determining the significance level = 0.05 (type I error = 5%, 2-sided) and power of the test = 80% (type II error = 20%), 33 samples would be needed in each group

$$n = \frac{(Z_{\alpha/2} + Z_{\beta})^2 (\sigma^2)}{(\mu_1 - \mu_2)^2}$$

$n =$ samples would be needed in each group

$\alpha =$ type I error = 0.05 ($Z_{\alpha/2} = 1.96$)

$$\beta = \text{type II error} = 0.20 \quad (Z_{\beta} = 0.84)$$

σ = standard deviation

$\mu_1 - \mu_2$ = The difference of mean values between groups

$$n = \frac{(1.96 + 0.84)^2 (4.26^2)}{(5.92 - 2.89)^2} = 33$$

From the calculations, it was found that at least 33 samples were used per group. After add dropout rate 15%, So 40 samples are to be used per group, a total of 80 people in this study.

Statistical analysis

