8.8.2 Inferential statistics

- Comparison of changes in eGFR, serum phosphate, urine protein creatinine ratio, urine phosphate, urine β 2-microglobulin, AST, ALT, HBV DNA between the treatment with TAF and adjusted dose TDF for 48 weeks by using the Repeated measures ANOVA or Friedman's test.

- Comparison of the change in urine NGAL between the treatment with TAF and adjusted dose TDF for 48 weeks by using Independent T test or Mann whitney test

Data recording and analysis using SPSS programme

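### Both methods named for eGFR use only patients with every visit in their standard form, and the plan states no other handling of missing data; a mixed model in the same software would use all observed visits

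*Combined protocol and SAP*

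**What the plan says.** The visit table at the start of the protocol schedules creatinine, and so eGFR, at weeks 0, 12, 24, 36 and 48. Section 8.8.2 compares changes in eGFR, serum phosphate, the urine markers (NGAL is handled separately), AST, ALT and HBV DNA between arms "for 48 weeks by using the Repeated measures ANOVA", with Friedman's test as the alternative. On software it says only "Data recording and analysis using SPSS programme", without naming a procedure.

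The sample size section expects losses: "After add dropout rate 15%, So 40 samples are to be used per group". Under "Withdrawal or termination criteria" there are five reasons. One is a GFR criterion at 15 ml/min and one is renal replacement therapy. The others are liver or kidney transplant, the patient's own request, and HCC.

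The document gives no analysis population, no rule for missing values, no imputation, and no statement on how the earlier visits of a withdrawn patient are used.

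**The concern.** Classical repeated measures ANOVA needs all five eGFR values from a patient, and Friedman's test likewise needs complete blocks. Run in their usual form, either would leave out a patient who withdraws after week 24 altogether, including weeks 0, 12 and 24. A patient who misses only week 12 would lose a valid week-48 value.

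Two things are at stake. One is precision, because every isolated missed visit costs a whole patient. The other is validity. Some exits are triggered by the outcome on which the trial is sized, so completers need not represent the groups randomised. If patients with falling eGFR leave one arm more often, that arm's completer mean looks better than it should. The earlier eGFR values that could correct for this would have been collected but not used.

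**Working it through.** **Inputs from the plan.** Two-sided alpha 0.05 ("type I error = 5%, 2-sided"), power 80%, difference 5.92 − 2.89 = 3.03, SD 4.26, 33 evaluable and 40 enrolled per arm, 15% dropout.

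**Assumed, because the plan gives no figure.** Loss by arm, share of leavers who are eGFR-driven, between-visit correlation (0.6) and missed-visit rate per visit (2% to 5%).

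**1. The plan's own figure.** A two-sample t-test with difference 3.03 and SD 4.26 needs 32.02 per arm, rounded up to 33. This agrees with "33 samples would be needed in each group". (The formula as printed lacks a factor of 2 and gives 15.5; that is a separate point.) Inflating for dropout, 33 / 0.85 = 38.8, so 39; the plan enrols 40.

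**2. Power after 15% dropout.** 40 × 0.85 = 34 complete patients per arm, and t-test power is 82%. Dropout alone does not break the design.

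**3. Single missed visits.** If each of the four follow-up visits is missed at random with chance p, the share of the remaining 34 who lose at least one visit is 1 − (1 − p)^4.

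| p (assumed) | Share lost | Lost per arm | Complete per arm | t-test power |
|---|---|---|---|---|
| 2% | 7.8% | 2.6 | 31.4 | 79% |
| 5% | 18.5% | 6.3 | 27.7 | 74% |

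The power figures are for a two-sample comparison of the completers, which is the basis of the plan's own calculation.

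**4. Bias from eGFR-related loss.** Suppose the patients with the lowest week-24 change, a fraction q of an arm, leave. The completers' mean week-48 change then rises by correlation × SD × φ(z_q)/(1 − q), where φ is the normal density and z_q the normal q-quantile. Here correlation × SD = 0.6 × 4.26 = 2.556. The bias in the difference is the gap between the two arms' rises. When only one third of leavers are eGFR-driven and the rest leave at random, q is one third of the loss.

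| Loss by arm (assumed) | eGFR-driven share | φ/(1 − q), each arm | Shift in difference | % of 3.03 |
|---|---|---|---|---|
| 15% v 15% | all | 0.274, 0.274 | 0 | 0% |
| 20% v 10% | one third | 0.1385, 0.0768 | 0.0618 × 2.556 = 0.16 | 5% |
| 20% v 10% | all | 0.350, 0.195 | 0.155 × 2.556 = 0.40 | 13% |
| 25% v 5% | one third | 0.1673, 0.0422 | 0.1251 × 2.556 = 0.32 | 11% |
| 25% v 5% | all | 0.4237, 0.1086 | 0.3151 × 2.556 = 0.81 | 27% |

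The sign depends on which arm loses more. With 20% v 10% and all leavers eGFR-driven, 3.03 becomes 3.43 or 2.63. Simulated trials with the same inputs gave 3.42 and 2.63.

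**5. A likelihood analysis of all observed visits.** In the same simulations with SD 4.26, an estimate using the week-12 and week-24 values gave 3.02 to 3.03, with a standard error of about 1.05 against 1.02 for complete cases. Dropout was generated from observed week-24 values, which is the condition under which such a model is valid. The result shows what the method can recover, not that it is robust to every kind of loss.

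**The case against.** The strongest objection is that the plan is silent rather than wrong. It names a test and a package, not a procedure, and the sponsor may intend imputation or a mixed model. A reader might infer that the plan orders incomplete patients to be deleted. It does not; deletion is a property of the named methods in their standard form. That stands, and the point is worded accordingly.

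A second objection is that the 15% dropout figure itself implies bias in the eGFR comparison. A reader might infer this, but it does not follow. The plan applies one figure to both groups, and equal loss of the same kind gave no bias.

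Third, not every leaver need have a falling eGFR. HCC and a patient's own request are not eGFR triggers. The GFR criterion is ambiguously worded, as a reduction or a level, and appears to concern a level near 15 ml/min rather than a low change. The monitoring guidance answers GFR below 40 with monthly visits and below 30 with a change of drug, and neither is listed as a withdrawal criterion. Much renal decline would therefore bring more visits, not exit. This is why the case with all leavers eGFR-driven is given only as an upper end. Even its shift of 0.40 is about 0.4 of the simulated standard error (0.40 / 1.02).

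Fourth, the power cost of dropout is already covered. That stands for the stated 15%, but not for isolated missed visits.

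What remains is that neither named option makes use of incomplete patients, and nobody can know in advance that loss will be balanced between the arms.

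**Conclusion.** The point holds as a recommended improvement, not as a demonstrated bias. As written, the eGFR comparison rests on methods that in standard form use completers only, and nothing else in the plan covers incomplete patients.

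The likely cost in precision is about 3 to 6 patients per arm beyond the 15% allowance, if 2% to 5% of follow-up visits are missed. Bias requires eGFR-related loss that differs between arms. With 20% v 10% loss it is about 5% to 13% of the planned difference, depending on how many leavers are eGFR-driven. A more extreme 25% v 5% split would roughly double that. These figures rest on assumed loss rates, a between-visit correlation of 0.6 and the plan's SD of 4.26. They show a plausible size and do not predict what will happen in this trial.

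**What to change.** In section 8.8.2, for eGFR and the other continuous markers with a week-0 value:

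- Replace both repeated measures ANOVA and Friedman's test with a linear mixed model for repeated measures (SPSS MIXED), with arm, visit, arm-by-visit, baseline value and unstructured covariance. Transform skewed markers.
- Include every randomised patient with at least one post-baseline value, in the arm assigned, and report the week-48 contrast.
- Analyse HBV DNA separately. It is scheduled only at weeks 24 and 48, and entry requires 10 U/mL or less, so it has no week-0 visit value and sits near a floor.
- Report the number withdrawn and the reasons by arm.
- Give the complete-case result as a sensitivity analysis, together with one for data missing not at random, for example assigning unfavourable values after renal replacement or GFR-triggered withdrawal.

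The cost is a few sentences, in software already named, with no extra patients or visits. There are two downsides. The model relies on observed values explaining missingness, which is why the second sensitivity analysis is needed. Its standard error is also slightly larger than the complete-case one, about 1.05 v 1.02 in simulation.

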[figure not shown]
Randomized trial of
tenofovir disoproxil fumarate dose adjustment VS. switching to tenofovir alafenamide
in tenofovir disoproxil fumarate-experienced chronic hepatitis B patients with renal impairment

SIRB Protocol No. : 657/2562(EC3)

COA no. : SI 798/2019

Document date : 25 Nov 2019

Study protocol

| | Week 0 | Week 12 | Week 24 | Week 36 | Week 48 |
|---|---------------|----------------|----------------|----------------|----------------|
| History taking and physical examination | X | X | X | X | X |
| CBC | X | | | | X |
| Creatinine, BUN, Uric acid, Calcium, Phosphate, Electrolyte | X | X | X | X | X |
| AST/ALT | X | X | X | X | X |
| HBV DNA viral load | | | X | | X |
| urinalysis, urine protein creatinine ratio, urine phosphate | X | X | X | X | X |
| urine β 2-microglobulin | X | X | X | | X |
| urine NGAL | X | X | | | |
| ultrasonography of upper abdomen | | | X | | X |

- Some blood tests may be stored before -20 ° C for later tests.

- Some urine tests may be stored before -30 ° C for later tests.

Monitoring and follow-up guidelines in the event that patients receiving TDF dose adjustment or change to TAF and the kidney function deterioration.

- If the GFR from 40 ml/min or more: Make appointment for examination every 12 weeks

- If the GFR is less than 40 ml/min: Make appointment every month

- If the GFR is less than 30 ml/min: Change to Entecavir (1mg) 1 * 1 po pc

If patient will have to check up earlier than 12 weeks, there will be a travel cost of 300 baht per time.

However, if the patient comes to the same appointment every 12 weeks, there will be no travel cost.

Inclusion criteria

1. Age between 18 - 75 years old

2. Chronic hepatitis B virus infection

3. Reduced renal function and need to adjust the dose of TDF

4. Have an eGFR of ≥ 15 ml / min.

5. HBV DNA viral load levels ≤ 10 U/mL in the last 3 months before participating in the project

6. No HCC by ultrasonography of the upper abdomen or CT 3-phase of liver or MRI liver in the 3 months before participating in the project.

Exclusion criteria

1. HIV infection or hepatitis C or hepatitis D co-infection

2. Decompensated cirrhosis, including variceal bleeding, ascites, hepatic encephalopathy

3. Active hepatocellular carcinoma or during the 3 years after treatment

4. Solid organ transplantation or Bone marrow transplantation

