8.8.1 Descriptive statistics

Demographic data such as qualitative variables such as gender, presented in frequency and percentage.

The quantitative variables, such as age, that are continuous data, presented with the mean and standard deviation (SD) if the data has a normal distribution. However, if the data doesn't have a normal distribution, presented with the median and minimum-maximum values.

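### Friedman's test, one of the two methods named for eGFR and seven other outcomes, cannot compare the arms; for the other, repeated-measures ANOVA, no term, contrast, estimate or confidence interval is named.

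*Combined protocol and SAP*

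**What the plan says.** Section 8.8.2 (Inferential statistics) has two analysis lines.

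- The first covers eight outcomes: eGFR, serum phosphate, urine protein creatinine ratio, urine phosphate, urine β2-microglobulin, AST, ALT and HBV DNA. The stated aim is to compare changes "between the treatment with TAF and adjusted dose TDF for 48 weeks by using the Repeated measures ANOVA", with Friedman's test as the alternative: the choice of method reads "by using the Repeated measures ANOVA or Friedman" (Friedman's test).
- The second covers urine NGAL. It is to be compared between the same two arms "for 48 weeks by using Independent T test or Mann whitney test".

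The section does not say when Friedman's test would replace ANOVA. It also does not say which ANOVA term or contrast answers the question, or what estimate will be reported. The only normality rule is in section 8.8.1, where a variable that does not "have a normal distribution, presented with the median and minimum-maximum values". That rule is written for descriptive summaries.

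The Sample size calculation rests on a difference between two group means. It sets a TAF change of +2.89 against a hospital observation that "the mean The eGFR change value level is +5.92 after TDF dose adjustment", with SD 4.26, two-sided 5% significance and 80% power. The result is 33 per group, and then "After add dropout rate 15%, So 40 samples are to be used per group".

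**The concern.** The aim is a between-arm comparison, but one of the two methods offered for eight outcomes has no place for the arm. If it is used, its p-value says whether values moved over the visits, not whether TAF and adjusted-dose TDF differ. The plan's own figures have eGFR rising in both arms, so a significant result would be almost certain and could be reported as a treatment difference when there is none.

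The ANOVA option has a lesser fault. It offers several tests (arm, visit, arm-by-visit), and the plan picks none. A reader cannot tell which result is the trial's main answer for eGFR, or whether the difference used for the sample size will be reported with a confidence interval.

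**Working it through.** **Inputs.** From the Sample size calculation: changes of +5.92 and +2.89, SD of change 4.26, two-sided 5%, power 80%, 40 per group, 15% dropout. From the visit schedule: creatinine, the source of eGFR, at weeks 0, 12, 24, 36 and 48. Assumed for the simulations: normal data, equal correlation between visits, and a change that is linear, immediate or at week 48 only.

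**1. The plan's own figure.** The difference is 5.92 - 2.89 = 3.03. The two-sample formula is n = 2(1.96 + 0.84)² × 4.26² / 3.03² = 31.0 per group. The t-based solution is 32.02, rounded up to 33, so the stated 33 agrees. (The formula as printed lacks the factor 2 and gives 15.5; that is a separate matter.) After dropout, 40 × 0.85 = 34 per group. Power for a two-sample t-test on change is 81.2% at 33 and 82.4% at 34. The trial is therefore sized for a difference in mean change between two arms.

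**2. What Friedman's test uses.** With N patients and k visits, rank each patient's k values from 1 to k and let R_j be the rank sum at visit j. The statistic is

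χ² = [12 / (N k (k + 1))] × Σ R_j² - 3N(k + 1).

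The arm label appears nowhere. Exchange the labels TAF and TDF among patients in any way and the statistic is unchanged, so it cannot be evidence about the arms.

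**3. Size of the effect, as an illustration.** Proportion of simulated trials with p < 0.05, 34 per arm:

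| True change in the two arms | Difference | Friedman, arms pooled | Mann-Whitney on week-48 change |
|---|---|---|---|
| +5.92 / +2.89 (plan's values) | 3.03 | 100% | 79-82% |
| +2.89 / +2.89 | 0 | 99.6-100% | about 5% |
| +1.515 / -1.515 (illustrative) | 3.03 | about 4-6% | about 79-82% |

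The Mann-Whitney figures depend only on the difference. Running Friedman's test separately in each arm does not help. Under the plan's values it is significant in both arms in 88-96% of trials and in one arm only in 4-12%. With no difference (both +2.89), it is significant in one arm only in 8-20%. That contrast is more frequent when the arms do not differ than under the plan's values.

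**4. What ANOVA contains.** The arm-by-visit term allows the contrast

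(week 48 - week 0, TDF) - (week 48 - week 0, TAF) = 5.92 - 2.89 = 3.03.

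At 34 per arm its standard error is 4.26 × √(2/34) = 1.03. A 95% interval at the plan's values would be 3.03 ± 2.00 × 1.03, or about 1.0 to 5.1. This is the quantity behind the sample size, but section 8.8.2 does not name it. Two other tests are open under the same wording:

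- The main effect of arm averages in the baseline visit. In simulation with 33 per arm and an assumed between-patient SD of 10, it had 6-16% power.
- The omnibus arm-by-visit test (4 degrees of freedom) has 74% power if the effect is linear and 85% if it is immediate or late.

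**5. The NGAL line.** The independent t-test and Mann-Whitney test are a matched parametric and rank pair for two arms. The plan therefore already holds a rank method that makes the intended comparison.

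**The case against.** Nothing in the plan rescues Friedman's test as a between-arm comparison. The case on the other side concerns ANOVA and the size of the consequences, and much of it stands.

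- *A reader might infer that repeated-measures ANOVA cannot give the sized difference.* The documents do not support this. The contrast in step 4 of the working is exactly that difference. The fault is that it is not named, not that the method is wrong.
- *A reader might infer that the ANOVA route is underpowered.* Section 8.8.2 does not commit to the omnibus test. Under equal correlation between visits, that test falls below the 82% of the week-48 difference only for a linear effect. With correlation that decays over time, a check gave 77-80% (linear) and 94-96% (immediate or late). No general power deficit is shown.
- *A reader might infer a serious loss from patients with missed visits.* Classical ANOVA does drop incomplete patients, but the documents give no missed-visit rate and do not say which losses the 15% covers. Any figure would rest on assumed rates, so it is not part of the error.
- *The simulations use normal data, whereas Friedman's test would more naturally be applied to skewed outcomes.* This is correct. The percentages show the mechanism and do not predict this trial's error rate. The argument from the formula needs no distribution.
- *Week 48 is not stated in the sample size text.* This is also correct. It is inferred from the 48-week comparison in section 8.8.2.

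**Conclusion.** The point on Friedman's test holds as written and without distributional assumptions: a method with no arm factor is named for a between-arm comparison of eight outcomes. In the illustration it is significant in about 100% of trials with or without a treatment difference when both arms rise, and in about 4-6% when a true difference of 3.03 comes from opposite changes.

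The point on ANOVA holds only as under-specification. No term, contrast, estimate or confidence interval is named, so the analysis is not tied to the difference of 3.03 (SD 4.26) that gives 33 per group. The sample size itself is unaffected: the week-48 difference has 82% power at 34 per arm.

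The plan should be amended. Confidence is high on Friedman's test. On ANOVA the conclusion is limited to what the text leaves open.

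**What to change.** 1. **Replace Friedman's test** with the Mann-Whitney test on change from baseline, as already named for NGAL, and state when it is used instead of the parametric method. Where a week-0 and a week-48 value are both scheduled, use the change between them.
2. **Name one main eGFR result**: the between-arm difference in mean change from week 0 to week 48, with 95% confidence interval. Either of two routes is adequate:
   - a t-test or baseline-adjusted ANCOVA on all patients with a week-48 value;
   - a mixed model with arm, visit and arm-by-visit in SPSS, using all available values.

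   Baseline adjustment is an optional gain in precision, not the correction of an error.
3. **State week 48** as the time point in the Sample size calculation, so that it matches the analysis.
4. **Treat HBV DNA separately.** The visit schedule has it at weeks 24 and 48 only, so change from baseline is not available from scheduled visits. Compare the week-24 and week-48 values between arms.

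The cost is analysis wording only, in the software already planned, with no new data or patients. If data are normal, Mann-Whitney gives up about 2 points of power against the t-test (79-82% against about 82-84% for a difference of 3.03).

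### Friedman's test, the named alternative for eGFR and seven other outcomes in section 8.8.2, has no arm term and cannot compare TAF with adjusted-dose TDF

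*Combined protocol and SAP*

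**What the plan says.** The first bullet of section 8.8.2 opens with "Comparison of changes in eGFR, serum phosphate, urine protein creatinine ratio" and goes on to urine phosphate, urine β2-microglobulin, AST and ALT. It closes with "HBV DNA between the treatment with TAF and adjusted dose TDF for 48 weeks by using the Repeated measures ANOVA or Friedman's test". That makes eight outcomes, one stated contrast (TAF against adjusted-dose TDF) and two candidate methods. No ANOVA term is named, and no rule says when the alternative applies.

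The second bullet deals with urine NGAL separately: "Comparison of the change in urine NGAL between the treatment with TAF and adjusted dose TDF for 48 weeks". The method given for it is a two-group comparison, either parametric or rank-based: "by using Independent T test or Mann whitney test".

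The schedule table gives creatinine, from which eGFR would be derived, at all five visits: "Creatinine, BUN, Uric acid, Calcium, Phosphate, Electrolyte | X | X | X | X | X". Urine NGAL is marked at weeks 0 and 12 only. HBV DNA is marked at weeks 24 and 48 only: "HBV DNA viral load | | | X | | X". Inclusion criterion 5 requires "HBV DNA viral load levels ≤ 10 U/mL in the last 3 months before participating in the project".

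The sample size section is built on change in eGFR. It takes +2.89 (SD 4.26) for TAF from the literature and, for dose-adjusted TDF, the hospital's own observation: "The eGFR change value level is +5.92 after TDF dose adjustment".

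**The concern.** The question in the first bullet is whether two independent groups of patients change differently. Friedman's test is a one-sample procedure for repeated measurements: it asks whether the visits differ from one another within patients. If the data are judged non-normal and it is used, a significant eGFR result would show only that eGFR moved over time. Because the protocol expects both arms to improve, such a result is nearly assured and could be reported as a treatment difference. Running the test in each arm separately does not help, since two within-arm p-values are not a comparison of arms.

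Two lesser mismatches sit in the same section. An NGAL result described as covering 48 weeks would rest on samples from the first 12. For HBV DNA, the plan speaks of changes without naming the value from which change is measured, the ANOVA term or the scale.

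**Working it through.** **1. The planning figures.** Difference 5.92 − 2.89 = 3.03; SD 4.26; two-sided 5% level; 80% power; 33 per group, 40 after dropout. An exact two-sample t calculation gives power 79.98% at 32 per group and 81.2% at 33, so the stated 33 is reproduced. Dropout: 33 / 0.85 = 38.8, so 39 against the stated 40. (The formula as printed evaluates to 15.5 because it lacks the factor 2; that is a separate matter and does not affect this point.) The sample size therefore presupposes a two-group comparison of change.

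**2. What Friedman's test uses.** For each patient the visits are ranked 1 to k; the statistic depends only on the rank sums per visit. Arm does not enter. As a check, data for 40 + 40 patients at five visits were analysed, the arm labels were shuffled, and the test was repeated: p = 0.000293 both times. This is a property of the test and depends on no assumption about the trial.

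**3. Consequence for eGFR.** Simulation inputs from the protocol: weeks 0, 12, 24, 36 and 48; SD of the week 0 to 48 change 4.26; 33 or 40 per arm. Assumed: full change reached by week 12 or linear to week 48; visit errors independent or autoregressive (0.7); 3,000 to 4,000 trials per case. Percentage of trials significant at 5%:

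| True change in the two arms | Friedman, pooled | Mann-Whitney on change |
|---|---|---|
| +5.92 and +2.89 (planned) | about 100% | 79% to 87% |
| +2.89 and +2.89 (no arm difference) | 99.6% to 100% | 4% to 6% |

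The two Friedman entries cannot be told apart, although the arms differ in the first row and not in the second. Mann-Whitney on the change separates them. Run within each arm in the planned case, Friedman's test is significant in about 100% of trials in the +5.92 arm and about 87% to 98% in the +2.89 arm (independent errors). Usually both arms are significant and the difference remains untested.

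**4. NGAL.** Scheduled samples: weeks 0 and 12. The longest change available is 12 of the 48 weeks. The tests named in that bullet do compare arms and suit a single change per patient.

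**5. HBV DNA.** Scheduled samples: weeks 24 and 48. On these alone, an arm-by-time term measures only the change from week 24 to week 48. Suppose, purely as an assumption, 6 patients in one arm and none in the other rebound to 1,000 U/mL before week 24 and stay there, with all others at 10. The week 24 to 48 change is then zero for everyone and the interaction sees nothing. The arm main effect gives p = 0.0097 (33 per arm) or 0.0105 (40 per arm), and the change from the pre-entry value to week 48 gives the same p. The scale matters too: with the same 6 against 0, a raw-scale test of change gives p between 0.010 and 0.23 according to how the assumed rebound sizes are spread.

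**The case against.** Repeated measures ANOVA is named first and can carry arm and arm-by-time terms. A reader might infer that the eGFR comparison as a whole is invalid. The documents do not support that: the fault is confined to the nonparametric branch, and the ANOVA branch needs only its term named. What stands is that 8.8.2 gives no rule for choosing between the branches, and 8.8.1 ties normality only to descriptive summaries. Use of the Friedman branch cannot be ruled out.

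A reader might also infer that Friedman's test would hide a true difference. That occurs if the arms move in opposite directions: at +1.515 and −1.515 (the same gap of 3.03) the pooled test is significant in only 4% to 6% of trials. But the protocol plans for both arms to rise. Even in the opposite-direction case, Friedman's test run by arm is significant in roughly 31% to 67%, and the plan does not say whether it would be pooled. On the planning figures the danger is a positive result that cannot be interpreted, not a missed difference.

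For NGAL, the 48 weeks can be read as the length of treatment, and the separate bullet with a two-group test suggests that the authors knew there was one change per patient. The documents therefore do not establish a contradiction, only an ambiguity.

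For HBV DNA, it is tempting to say that no baseline exists. It does: every eligible patient has a value of at most 10 U/mL from the 3 months before entry. A persistent rebound would also show in the arm main effect. The rebound numbers used above are invented, as the documents give no rebound rate. What stands is that baseline, term and scale are not stated.

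**Conclusion.** The concern holds for Friedman's test. As the named alternative for a between-arm comparison of eight outcomes, including the one that sizes the trial, it cannot answer the question asked. With eGFR rising in both arms as the protocol expects, it is significant in about 100% of simulated trials when pooled, whether or not the arms differ; Mann-Whitney on the change rejects in about 5% when they do not. The percentages rest on the assumed visit patterns and error structure; the absence of an arm term does not. The effect is conditional on the nonparametric branch being used. This should be corrected before analysis. The NGAL and HBV DNA items are clarifications of wording to be made at the same time and would not carry this weight alone.

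**What to change.** - **First bullet, alternative test:** replace Friedman's test with Mann-Whitney on the change from baseline to week 48, a test that 8.8.2 already names for NGAL. The drawback is that it does not use weeks 12 to 36.
- **First bullet, ANOVA:** state that the arm-by-time term answers the between-arm question for outcomes measured at week 0, and say when the nonparametric alternative applies.
- **NGAL:** describe the result as the change from week 0 to week 12. The tests stay as they are.
- **HBV DNA:** name the pre-entry qualifying value as baseline. In place of a raw-scale ANOVA, compare by arm the proportion above 10 U/mL at weeks 24 and 48, with a 95% confidence interval for the difference (Newcombe's method, for example). The interval should carry the interpretation, because power is low when rebounds are rare: 0 against 0 gives ±10.4 percentage points at 33 per arm and ±8.8 at 40, and 5 against 0 gives an exact p of 0.053 to 0.055.

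The cost is a change of analysis wording, on data already scheduled or already required at entry. No visits, assays or patients are added, and the sample size is unaffected.

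### Urine NGAL change is compared without adjusting for the week-0 value; the planned t-test is valid, but ANCOVA would usually be more precise at almost no cost

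*Combined protocol and SAP*

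**What the plan says.** Section 8.8.2 (Inferential statistics) gives urine NGAL its own line: "Comparison of the change in urine NGAL between the treatment with TAF and adjusted dose TDF for 48 weeks by using Independent T test" or a Mann-Whitney test. Neither that line nor the rest of the plan names a baseline covariate, ANCOVA or any other adjustment. The other eight outcomes in 8.8.2 are assigned to repeated measures ANOVA or Friedman's test.

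The schedule table under Study protocol marks urine NGAL at week 0 and week 12 and at no later visit. NGAL is the only outcome in 8.8.2 with a single measurement after baseline.

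The Sample size calculation section rests on eGFR change alone. It sets "significance level = 0.05 (type I error = 5%, 2-sided") and "power of the test = 80% (type II error = 20"%), arrives at 33 per group, and then states: "After add dropout rate 15%, So 40 samples are to be used per group, a total of 80 people in this study". The documents give no SD, correlation, effect size or power for NGAL.

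**The concern.** With one baseline and one follow-up value per patient, the inference on NGAL rests on a single between-arm comparison. A change score fixes the weight given to baseline at exactly 1. ANCOVA estimates that weight from the data. Unless the true regression slope of follow-up on baseline is close to 1, the fixed weight adds noise, and an arm that happens to start higher will tend to show a larger fall whatever the treatment does. What is at stake is the width of the NGAL confidence interval and the chance of detecting a real difference, using samples the trial collects anyway.

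The same line also describes the comparison over 48 weeks, while the schedule allows an NGAL change to be computed only from week 0 to week 12.

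**Working it through.** **The plan's own figure.** This is for eGFR, but it fixes the group size used below. Inputs from Sample size calculation: difference 5.92 − 2.89 = 3.03, SD 4.26, two-sided alpha 0.05, power 80%.
- The formula as printed has no factor 2: (1.96 + 0.84)² × 4.26² / 3.03² = 15.5, which does not give 33.
- With the factor 2 for two groups it gives 30.99. The t-based solution is 32.02, which rounds up to 33. The stated 33 is therefore reproduced by the standard two-sample calculation.
- Dropout: 33 / 0.85 = 38.8, so 39 against the stated 40.
- Patients left after dropout: 40 × 0.85 = 34 per arm.

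The missing factor 2 is a separate matter and has no bearing on NGAL.

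**Precision of the two NGAL analyses.** Let s0 and s1 be the SDs at weeks 0 and 12, and ρ their correlation.
- Change score, variance per patient: s0² + s1² − 2ρ·s0·s1.
- ANCOVA, variance per patient: s1²(1 − ρ²).
- Difference: (s0 − ρ·s1)², which is never negative and is zero only when the slope ρ·s1/s0 equals 1.
- With equal SDs, the ratio ANCOVA/change is (1 − ρ²) / [2(1 − ρ)] = (1 + ρ)/2.
- Estimating the slope multiplies the ANCOVA variance by about 1 + 1/(2n − 4). With n = 34 this is 1 + 1/64 = 1.016.

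**Power.** Fix the effect so that ANCOVA has 80% power, and let R be the variance ratio including the penalty. The power of the change-score t-test is then Φ(2.80·√R − 1.96), where 2.80 = 1.96 + 0.84. ρ is assumed over a range.

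| ρ (assumed) | (1 + ρ)/2 | R with penalty | Variance reduction | Change-score power when ANCOVA has 80% |
|---|---|---|---|---|
| 0.3 | 0.65 | 0.66 | 34% | 62% |
| 0.5 | 0.75 | 0.76 | 24% | 69% |
| 0.7 | 0.85 | 0.86 | 14% | 74% |
| 0.9 | 0.95 | 0.96 | 4% | 79% |

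**Simulation check.** With 34 per arm, normal data, equal SDs and 10,000 runs per setting, the effect was set so that the change-score test should have about 80% power. The change-score test reached 0.79 throughout. ANCOVA reached 0.93, 0.89, 0.85 and 0.80 at ρ = 0.3, 0.5, 0.7 and 0.9. With no effect, both methods rejected in 4.6% to 5.3% of runs.

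**Unequal SDs.** For s1/s0 between 0.7 and 1.5 and the same four correlations, the large-sample variance ratio runs from 0.41 to almost 1.00. The direction holds, but the size depends strongly on quantities the documents do not give.

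**Chance imbalance.** With 34 per arm, the between-arm difference in mean baseline has an SD of √(2/34) = 0.24 in units of the patient SD. An imbalance of at least 0.25 SD in either direction therefore occurs in about 30% of such trials. At ρ = 0.5 and equal SDs, a 0.25 SD imbalance shifts the change-score comparison in that trial by (1 − 0.5) × 0.25 = 0.125 SD.

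**The case against.** The strongest reply is that this is a preference about efficiency, not an error. A reader might infer from the missing covariate that the planned test is biased or that baseline is ignored. The documents support neither. The change score uses the week-0 value by subtraction. Under randomization its comparison is unbiased on average, and the simulation shows a correct type I error. Chance imbalance moves the estimate in a particular trial, but the standard error already allows for it. This part of the objection stands in full.

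A reader might also conclude that a change score is always at least as variable as ANCOVA. That is true in large samples. At 34 per arm with equal SDs, the slope penalty cancels the gain when (1 + ρ)/2 × 65/64 = 1, that is at ρ of about 0.97, and reverses it above that. Nor do the documents show that the loss is large: they give no NGAL correlation, and at ρ = 0.9 it is about one power point. This too stands.

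Three further limits are fair:
- The calculation compares two analyses on the same scale. It does not evaluate the Mann-Whitney branch, nor a move from raw change to a log-scale ratio, which is a different estimand. Nothing in the documents dictates logs.
- NGAL is one of nine outcomes in 8.8.2, and no power was ever claimed for it.
- Leaving the choice between a parametric and a rank test open is not peculiar to NGAL. The preceding line of 8.8.2 does the same for eight outcomes, and 8.8.1 has a normality rule for descriptive summaries.

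On the 48-week wording, the phrase can be read as describing the duration of treatment rather than the NGAL interval. Even so, it leaves the interval unstated. It needs reconciling, but it is separate from the question of precision.

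What survives is that the baseline value is already collected and, over most plausible correlations, adjusting for it buys precision for a change of wording.

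**Conclusion.** The point holds as a recommendation on efficiency. The planned t-test is valid, but it is generally less precise than a baseline-adjusted comparison and does not correct for chance baseline imbalance. With equal SDs and 34 per arm, adjustment cuts the variance by about 34%, 24%, 14% and 4% at correlations of 0.3, 0.5, 0.7 and 0.9. The direction is secure except at correlations very near 1. The size rests on the assumed correlation and equal SDs and cannot be fixed from the documents.

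It would be wrong to infer that the sample size is affected. The 33 and 40 per group rest on eGFR and do not change. Nothing in the documents ties a decision or the trial's main conclusion to NGAL.

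**What to change.** Replace the NGAL line in 8.8.2 with the following:
- **Main analysis:** ANCOVA of week-12 NGAL on arm and week-0 NGAL, reporting the adjusted difference with its 95% CI.
- **Scale:** prespecify a log transform of both values if they are positive and skewed, with a stated rule for values below detection. Results are then reported as a ratio of geometric means with 95% CI.
- **Sensitivity analysis:** the Mann-Whitney test on the change.
- **Interval:** reconcile the 48-week wording with the schedule. As the schedule stands, the outcome is the change from week 0 to week 12 and should be labelled so.

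The cost is a few lines of wording. No extra patients or samples are needed, and SPSS, the package named in the plan, fits the model. If the log scale is used, the result becomes a ratio rather than a difference, and the rule for values below detection has to be written before the data are seen.
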